10.2. The Number of Participants

From two previous studies evaluating the utility of PA views in 15 degrees flexion compared with AP standing for long term evaluation of progression of knee arthritis the difference in mean joint space width measured on Lyon Schuss and AP standing views is between 0.63mm with a population standard deviation of 1.1. This gives an effect size of 0.57. At a power of 0.8 and significance level of 0.05 using the Altman nomogram the required sample size would be 100 patients. From audit it has been identified that 50% of patient from clinic will be treated with surgery. In addition to allow for errors in xray alignment making interpretation not valid an additional 25 patients will be added giving a sample size of 225 patients.

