When deciding between UKR and TKR the detection of the degree and pattern of arthritis is of critical importance. UKR are known to perform poorly in partial thickness disease and require full thickness cartilage in the retained tibiofemoral compartment[7, 8]. To establish whether a patient meets the indications for UKR x-rays are used with stress views being the gold standard, as well as the standard assessment that the studies of long term outcomes on UKR are based. Gibson and Goodfellow, who were first to describe stress x-rays in the workup of a patient for UKR, reported that those patients with a joint space width of more than 5mm in the lateral compartment had intact lateral cartilage during surgery making them appropriate for UKR [9]. More recently Waldstein *et al.* reported that patients with a lateral joint space width of more than 4mm may be appropriate for UKR however overall they noted poor correlation between joint space width measured on valgus stress views and intra-operative Outerbridge grade[10].

In addition to the low quantity of evidence regarding the relationship between stress views and intra-operative status of the joint the feasibility of performing stress x-rays also limits their use. Stress x-rays are resource dependent, can be uncomfortable for patients and require an additional practitioner. As such they are often not performed with many clinicians adopting alternative x-ray views, MRI or direct observation via arthroscopy [11]. It has been proposed that standing views with the knee in 15 degrees then 45 degrees flexion may load the medial and lateral compartments respectively and that these views may be an alternative to stress views without the requirement for an additional practitioner. However the outcomes based on these forms of assessment, and the relationship between the joint space width measured using these contemporary techniques has not been reported. An alternative would include a stress device that allows a stress x-ray to be performed without the requirement of the clinician.

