4. OBJECTIVES AND OUTCOME MEASURES/ENDPOINTS

Objectives	Outcome Measures
Primary Objective 
 • To assess the accuracy of different xray views of measuring joint space width within each compartment within the knee. 	Joint space width in the medial and lateral tibiofemoral compartments of the knee measured in mm.
Secondary Objectives 
 • To define the sensitivity and specificity of four different xray views at predicting bone on bone arthritis and joint space narrowing within each of the knee compartments and suitability for UKR. • To define the sensitivity and specificity of MRI at predicting suitability for UKR. • To assess the sensitivity and specificity of different xray techniques at inferring the status of soft tissue structures (anterior cruciate ligament and medial collateral ligament) within the arthritic knee. 	
A joint space width of 0mm will be classified as bone on bone arthritis, >0mm to <5mm will be classified as joint space narrowing and $\geq 5\text{mm}$ will be classified as full thickness cartilage. The sensitivity and specificity of each technique, at detecting each disease state in each compartment, compared to the gold standard of stress views will be recorded.
 
The sensitivity and specificity of MRI, compared to the gold standard of stress views, at predicting the status of each compartment will be recorded.
 
In patients proceeding to joint replacement as part of their standard clinical pathway the sensitivity and specificity of different xray techniques at inferring the status of soft tissue structures (anterior cruciate ligament and medial collateral ligament) within the arthritic knee will be compared to operative findings.

Tertiary Objectives 
 • To develop a decision aid to help clinicians decide between likelihood of a patient being a candidate for UKR based on pre-operative xray and MRI findings. 	The findings from this study will be used to develop a decision aid. The sensitivity and specificity of this decision aid will be calculated in the cohort of patients undergoing surgery using intra-operative audit findings as the gold standard.

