7. STUDY PROCEDURES

- Screening and consent (performed at clinic appointment) - 10 minutes
- Standard Clinical Xrays
 - Standing anteroposterior view
 - Lateral view
 - Patellofemoral view
 - Valgus stress view (clinician performed or using validated device)
 - Varus stress view (clinician performed or using validated device)
- Research xrays (performed at the same time as routine clinical xrays) – 10 minutes
 - Standing posteroanterior (PA) view 15 degrees flexion
 - Standing posteroanterior (PA) view 45 degrees flexion
- MRI (performed during a separate appointment at the patients convenience) – 30 minutes
- Measuring of routinely retrieved joint surface cartilage (performed in research laboratory)

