7.4. Baseline Assessments

At baseline a patient name, gender and date of birth will be recorded, together with hospital and NHS number will be recorded on the patient data sheet which will be linked to the CRF by way of a study number.

Research xray views will also be performed during the baseline assessment. In addition to routine clinical xrays: standing anteroposterior, lateral, skyline views and valgus/varus stress xrays two research xray views will be performed.

These two views are with the patient standing, hands resting on a frame for stability. The xrays are taken in the postero-anterior direction. The first of these standing views is taken with the knees flexed to 15 degrees, the second with the knees flexed to 45 degrees.

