10. STATISTICS AND ANALYSIS

10.1. Description of Statistical Methods

Joint space width of each of the compartments will be measured on each routine and research xray views taken using a standardised technique using custom software (Matlab, Massachusetts, USA). To compare the accuracy and agreement of different radiological views at measuring joint space width statistical methods for assessing agreement between two methods of clinical measurement as described by Bland and Altman will be used with stress views defined as the gold standard for comparison [12, 13].

For the secondary outcomes each of the compartments on each of the xray views will be classified as demonstrating bone on bone arthritis, full thickness cartilage or narrowing of joint space width. The sensitivity and specificity of each of the views at predicting each of these disease states will be compared with stress views which will be defined as the gold standard. The sensitivity and specificity of each of the views at predicting suitability for UKR will be calculated based on pre-defined indications of UKR.

The sensitivity and specificity of MRI at predicting suitability for UKR, based on pre-defined xray derived indications as the gold standard will be calculated.

The sensitivity and specificity of different xray techniques at inferring the status of soft tissue structures (anterior cruciate ligament and medial collateral ligament) within the arthritic knee will be evaluated against both MRI and intra-operative findings.

A decision aid will be developed based on the findings of this research and the sensitivity and specificity of this decision aid at predicting suitability for UKR will be calculated. Further work will then be performed to validate this scoring system.

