11.2. Data Recording and Record Keeping

A password protected database containing patient identifiable information solely for identifying patients who have subsequently had surgery and for collecting the results of intraoperative findings will be kept on a secure university computer. This database will be securely destroyed six months following the end of the study. No other patient identifiable information will be kept.

Xrays and MRI images will be measured in duplicate using pre tested software (Matlab, Massachusetts, USA) with the evaluator blinded to other images in that patients series as well as the final treatment outcome.

The majority of data will be generated electronically and it will be stored and backed up securely within the research institute. Where data is required to be transcribed from a paper pro forma this information will be checked by an independent member of the research team. Data will be analysed using Stata version 13 (Texas, USA).

Data will be retained for 10 years in line with our organisations policy.

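### The 100 patients in Section 10.2 fit two independent groups although the views are paired, and the stated power does not describe the primary agreement analysis against stress views

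*Combined protocol and SAP*

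**What the plan says.** Section 10.2 takes its inputs from two previous studies: "the difference in mean joint space width measured on Lyon Schuss and AP standing views is between 0.63mm", with an SD of 1.1 described as a population value, giving an effect size of 0.57. It then states: "At a power of 0.8 and significance level of 0.05 using the Altman nomogram the required sample size would be 100 patients". A 50% surgery share from audit and 25 further patients for misaligned x-rays bring the total to 225.

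Section 10.1 gives the primary analysis. Joint space width is measured in each compartment on each view, and Bland-Altman methods "will be used with stress views defined as the gold standard for comparison". No test of the 15-degree PA view against the standing AP view is listed.

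The imaging is within-patient. Section 7.4 says: "In addition to routine clinical xrays: standing anteroposterior, lateral, skyline views and valgus/varus stress xrays two research xray views will be performed". Section 7 lists the two research views, the first being "Standing posteroanterior (PA) view 15 degrees flexion".

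**The concern.** A sample-size statement should describe the analysis that the study will report, under the design that will produce the data. Section 10.2 appears to miss on both counts. The number 100 looks like a two-group total, whereas each patient supplies all the views. The contrast that is sized is a mean difference between two candidate views, whereas the primary analysis estimates the agreement of each candidate with stress views.

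What is at stake is the justification of 225. A reader of Section 10.2 cannot tell how precisely the bias and the limits of agreement against stress views will be estimated, and that is the primary result.

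**Working it through.** **Inputs.** From Section 10.2: difference 0.63 mm, SD 1.1 mm, effect size 0.57, power 0.80, significance level 0.05, surgery share 50%, allowance 25. Sidedness is not stated; two-sided is assumed. The documents give neither the correlation between views nor the SD of differences from stress views, so both are varied below.

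**1. Reproducing the plan's figure.** Effect size: 0.63/1.1 = 0.573, stated as 0.57.

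Two independent groups, normal formula: n per group = 2 × ((1.960 + 0.842)/0.57)² = 48.3, so 49 per group and 98 in total. The t-based version gives 49.3, so 50 per group and **100 in total**. The one-sided normal version gives 76 in total.

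Chain: 100/0.5 = 200, and 200 + 25 = 225. Both stated figures are reproduced.

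**2. The same contrast with paired data.** Normal formula: n = ((1.960 + 0.842) × SD_diff/0.63)². The sizes below are t-based.

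- If 1.1 mm is the SD of within-patient differences: 24 by the normal formula, 26 t-based (27 at the rounded effect size of 0.57).
- If 1.1 mm is the SD of a single view, the same for both views: SD_diff = 1.1 × √(2(1 − ρ)).

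| ρ (assumed) | SD_diff (mm) | Pairs needed | Power with 100 pairs |
|---|---|---|---|
| 0 | 1.556 | 50 | 0.980 |
| 0.3 | 1.302 | 36 | 0.998 |
| 0.5 | 1.100 | 26 | >0.999 |
| 0.7 | 0.852 | 17 | >0.999 |
| 0.8 | 0.696 | 12 | >0.999 |

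No paired reading with ρ ≥ 0 comes near 100. Through the protocol's own chain, 50 pairs would give 50/0.5 + 25 = 125, and 26 pairs would give 26/0.5 + 25 = 77.

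**3. Relation to the primary analysis.** Within a patient and compartment, (15-degree − stress) − (AP − stress) = 15-degree − AP. The sized contrast is thus the difference between two of the planned biases. It carries no information on the spread of either view about the stress view, on the 45-degree view, or on each compartment separately. The 1.1 mm therefore cannot stand in for the SD of differences from stress views.

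**4. Precision of the planned analysis.** Take n = 225 − 25 = 200 readable patients and one difference per patient per compartment, roughly normal with constant spread.

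- Bias: 1.96 × SD/√200 = 0.139 × SD.
- Each limit of agreement: 1.96 × SD × √(1/200 + 1.96²/(2 × 199)) = 0.237 × SD.

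| Assumed SD of differences (mm) | Half-width, bias (mm) | Half-width, each limit (mm) | Limits lie at bias ± (mm) |
|---|---|---|---|
| 0.5 | 0.07 | 0.12 | 0.98 |
| 1.0 | 0.14 | 0.24 | 1.96 |
| 1.5 | 0.21 | 0.36 | 2.94 |
| 2.0 | 0.28 | 0.47 | 3.92 |

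The SD range is purely an assumption. Section 3 says of the 15- and 45-degree techniques that "the relationship between the joint space width measured using these contemporary techniques has not been reported"; the sentence names no comparator, but no SD against stress views appears elsewhere either.

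**5. Operated subset.** 200 × 0.5 = 100 expected, with a binomial 95% range of 86 to 114 if the 50% is taken as exact. Section 7.3 counts excised surfaces only when replacement takes place within 6 months of screening. The audit share in Section 10.2 has no time window and refers to surgery in general. For retrieved tissue, 100 is therefore an upper expectation.

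**The case against.** The best defence is that Section 10.1 opens with the broad aim of comparing views, and that the sized contrast is the difference between two planned biases against the same reference. That stands. A reader might infer that the power belongs to something wholly foreign to the plan; the identity in step 3 shows that this goes too far. The link is only indirect, however, and does not reach the limits of agreement.

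Second, the two-group reading is inferred from arithmetic, because Section 10.2 names no groups. This is also true, but it is the reading that returns 100, and the paired readings do not.

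Third, correcting the figure removes the source of 225. This stands, and the fix must say so. A reader might conclude that enrolment should fall to 125 or 77. That does not follow, because those figures serve one contrast between two views and not the agreement analysis or the operative endpoints.

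Fourth, multiples of an unknown SD are generic, and normality may fail. Section 4 says "A joint space width of 0mm will be classified as bone on bone arthritis", and eligibility covers any grade, so values at 0 mm are to be expected. This limits the precision figures but does not remove the need to state them.

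Finally, a reader might treat the lack of a prespecified acceptable difference as part of the error. The stated aim can be read as ranking the views, and Section 4 already fixes cut-offs for the disease states. Such a margin would help but is optional.

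**Conclusion.** The point holds and should be fixed. The stated 100 is a two-independent-group total applied to paired views; the paired requirement is 26, or at most 50, depending on which SD 1.1 mm is. This assumes a two-sided 5% level and, for the upper figure, equal SDs and a non-negative correlation.

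A reader might infer that the study is underpowered. The documents do not support that: for the contrast named in Section 10.2 the error is conservative, with about 98% power or more from 100 pairs.

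The more important gap is that the stated power does not describe the primary Bland-Altman analysis. With about 200 readable patients, its precision is about 0.14 × SD for bias and 0.24 × SD for each limit, given roughly normal differences with constant spread. Whether that is adequate cannot be judged in millimetres from the documents, because they give no SD against stress views.

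**What to change.** (a) In Section 10.2, restate the basis for 225 as precision for agreement with stress views. Give about 200 readable patients and half-widths of about 0.14 × SD for bias and 0.24 × SD for each limit, in mm over an SD range labelled as assumed (for example 0.07 to 0.28 mm and 0.12 to 0.47 mm for SDs of 0.5 to 2.0 mm). State that one difference per patient per compartment is used. Section 11.2 says "Xrays and MRI images will be measured in duplicate using pre tested software", so the mean of the duplicates can serve. Note that compartments at 0 mm may break normality and constant spread.

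(b) If the power figure is kept, recompute it for paired data, say which SD 1.1 mm is, and add the paired contrast to Section 10.1.

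(c) Say openly that the paired figure no longer generates 225, and that 225 is kept on the strength of (a) and of the operated subset. Describe that subset as about 100 of 200 readable patients at the audit share, and as an upper expectation for retrieved tissue because of the 6-month window in Section 7.3.

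The cost is a rewritten Section 10.2 and, if the power figure is kept, one sentence in Section 10.1. No new procedures and no change to enrolment are needed.

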This study will evaluate the status of knee cartilage in 225 patients with varying degrees, and patterns, of knee OA using standing extension anteroposterior, 15 degrees flexion posteroanterior, 45 degrees flexion posteroanterior and valgus and varus stress views as well as MRI. These results will be compared to the gold standard imaging technique of stress views as well as to direct measurements of retrieved tissue in those patients who undergo knee replacement surgery. The sensitivity and specificity of each of the imaging techniques at predicting suitability for UKR will be calculated, the optimum imaging views proposed, and ultimately the results of this study will be used to develop a decision aid, based on optimum views, to help clinicians decide between likelihood of a patient being a candidate for UKR based on pre-operative x-ray and MRI findings.

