10.3. Analysis of Outcome Measures/Endpoints

Each image will be measured independently and statistical analysis will be performed blinded to the treatment outcome. Should a patient withdraw consent prior to termination of the study data that has been collected will only be used for analysis where, for each endpoint, a complete set of data is present.

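### Does the lack of a written rule for uninterpretable films put the choice of optimum view at risk?

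*Combined protocol and SAP*

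**What the plan says.** Section 10.2 builds the sample size from a comparison of two views, doubles it because half of clinic patients go on to surgery, and then says that "to allow for errors in xray alignment making interpretation not valid an additional 25 patients will be added", which brings the total to 225. It names no view and gives no failure rate.

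For the secondary outcomes, section 10.1 states that "each of the compartments on each of the xray views will be classified as demonstrating bone on bone arthritis, full thickness cartilage or narrowing" of the joint space, with stress views as the reference. Section 4 defines the classes by width. "A joint space width of 0mm will be classified as bone on bone arthritis", widths above 0 and below 5 mm count as narrowing, and 5 mm or more counts as full thickness. A film that cannot be measured fits none of the three.

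The only rule on incomplete data is in section 10.3. It says that data "will only be used for analysis where, for each endpoint, a complete set of data is present", and it applies to patients who withdraw consent. Section 11.2 has images measured in duplicate by an evaluator who is blind to the patient's other images and to the treatment outcome. Section 3 gives the purpose: "the optimum imaging views proposed, and ultimately the results of this study will be used to develop a decision aid".

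**The concern.** The plan foresees unreadable films and answers only with more patients. Extra patients restore precision. They do not make figures from readable films apply to every knee that was imaged, and they do not show which views failed.

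Failure could plausibly differ by view. The stated cause is alignment, and the views differ in positioning: standing in extension, standing at two flexion angles, and stressed by a clinician or a device. A view that reads well when it can be read, but often cannot, might then be preferred to one that gives a usable and correct answer in more knees. The stress views raise a second question, because a failed stress film removes the reference and not the test. At stake are the views to be recommended and the decision aid built on them. The primary Bland-Altman analysis is touched only in that its limits might be shown without the number of films that could not be measured.

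**Working it through.** **The plan's own figure.** Section 10.2 gives a difference that "is between 0.63mm with a population standard deviation of 1.1", so the effect size is 0.63/1.1 = 0.573, quoted there as 0.57. Take a two-sample comparison at 80% power and a two-sided 0.05 level (sidedness is not stated, so this is assumed):

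- n per group = 2 × (1.960 + 0.842)² / 0.57² = 48.3, so 49 per group and 98 in total. The t-based version gives 50 per group and 100 in total.
- 100/0.5 = 200, and 200 + 25 = 225, which reproduces the plan.
- 25/225 = 11.1% of patients.

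**Effect of counting failures.** Let s be sensitivity on readable films and f the failure rate, with failure unrelated to disease state. Sensitivity in all imaged knees, with a failed film counted as not correctly classified, is s(1 − f). The documents give neither s nor f, so these are assumed values for s = 0.90:

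- f = 2%: 0.90 × 0.98 = 0.882
- f = 11.1%/3 = 3.7% (allowance spread over three index views): 0.867
- f = 11.1% (whole allowance on one index view): 0.90 × 200/225 = 0.800

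If all failures fell on stress views, the index views would lose nothing by this reckoning.

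**When the order changes.** View A (0.90) falls below view B when f_A > 1 − s_B(1 − f_B)/0.90.

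| s_B | f_B = 0: threshold for f_A | Films of 225 | f_B = 5%: threshold for f_A |
|---|---|---|---|
| 0.88 | 2.2% | more than 5 | 7.1% |
| 0.86 | 4.4% | more than 10 | 9.2% |
| 0.85 | 5.6% | more than 12.5 | 10.3% |
| 0.80 | 11.1% | more than 25 | 15.6% |

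Against a 0.85 view with no failures, 13 failed films give 0.90 × 212/225 = 0.848. Against a 0.85 view with 4 failures, 17 failed films give 0.90 × 208/225 = 0.832 v 0.85 × 221/225 = 0.835. Against 0.80 with no failures, the whole allowance gives only a tie. With 5% failures on B, even the lowest threshold needs about 16 + 11 = 27 failed films, more than 25. Equal failure rates multiply every view by the same factor and never change the order.

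**Sampling error.** Suppose every one of 225 knees had the disease state. The 95% half-width around 0.90 is then 1.96 × √(0.90 × 0.10/225) = 0.039. With 112 such knees (assumed 50% prevalence) it is 0.056.

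Pairing the views on the same knees does not rescue the comparison. In the 13-film example, A is right and B wrong in at least 0.05 × 212/225 = 0.047 of knees. B is right where A failed in 0.85 × 13/225 = 0.049. The half-width for the difference is 1.96 × √(0.096/225) = 0.04, against a difference of 0.002.

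**Patients and films.** The 25 are patients, and each has five tibiofemoral views (standing, two flexed, two stress). Using 25 as a limit on failed films assumes one failure per affected patient. Whether the allowance was meant to include stress films is also an inference.

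**The case for a change.** The strongest case on the other side has three parts.

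First, the reversals above are small because they are computed at the crossing point. With the whole allowance on one view, 0.90 becomes 0.800 against an untouched 0.85, a gap of 0.05. This stands as arithmetic. However, a view that lost 25 of 225 films would show it in the denominator of its own sensitivity and specificity, and nothing in the documents suggests such a concentration.

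Second, failure may be related to disease. Suppose 20% of diseased knees are hard to read (sensitivity 0.60 v 0.95), and 50% of their films fail against 2% of the rest. Overall failure is then 11.6%. Sensitivity on readable films is (0.2 × 0.5 × 0.60 + 0.8 × 0.98 × 0.95)/0.884 = 0.910, against 0.880 if every film could be read. That is a real mechanism, but every input is assumed, and section 10.2 attributes failure to alignment, which is a technical fault.

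Third, a rule chosen after the results are seen could itself decide the ranking. The point is fair and argues for good reporting. It is softened by the blinding in section 11.2: if the evaluator judges readability while measuring, that judgement is made without sight of the other views or the outcome.

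What stands is that the plan has no written rule for a failed index or stress film.

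**Conclusion.** The gap is real but modest, and it lies in the secondary analyses. It is a missing detail that analysts would fill sensibly. They would leave out the failed film and keep the patient's other views, in the endpoint-by-endpoint spirit of section 10.3. They would treat a failed stress film as a missing reference for that compartment and give the number of unreadable films for each view.

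Whether a failed index film should also count as a misclassification is a fair trade-off. If failure is a technical fault unrelated to disease, accuracy on readable films is a valid quantity, and the yield of each view can be reported beside it. Combining the two is a convention and not a correction.

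A changed recommendation needs three things together: failed films dropped without account, failure rates that differ between views, and sensitivities that are close. The documents establish none of them. At the crossing points the differences are 0.002 to 0.003, against sampling error of about 0.04. The extreme loss of 0.10 requires all 25 failures on one view. Section 3 also judges the optimum protocol on acceptability to patients, number of films and resources, so a small difference in sensitivity would not settle the choice. The decision aid is checked against operative findings (section 4), with further validation planned (section 10.1). The primary analysis and the sample size of 225 are unaffected.
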